## **8.5. Pharmacokinetics**

- Whole venous blood samples will be collected for measurement of serum concentrations of lebrikizumab as specified in the SoA (Section 1.3).
- Samples may be collected at additional time points during the study if warranted and agreed upon between the investigator and the sponsor.
- Instructions for the collection and handling of biological blood samples will be provided by the sponsor. The actual date and time (24-hour clock time) of each sample will be recorded.

Intervention concentration information that may unblind the study will not be reported to investigative sites or blinded personnel until the study has been unblinded.

### **8.5.1. Bioanalysis**

Samples will be analyzed at a laboratory approved by the sponsor and stored at a facility designated by the sponsor. Serum concentrations of lebrikizumab will be assayed using a validated enzyme-linked immunosorbent assay method. Analyses of samples collected from placebo-treated participants are not planned. Bioanalytical samples collected to measure IP concentrations will be retained for a maximum of 2 years following last participant visit for the study. During this time, samples remaining after the bioanalysis may be used for exploratory metabolism studies or exploratory analyses such as bioanalytical assay validation or cross-validation exercises.

## **8.6. Pharmacodynamics**

Samples collected (as specified in the SoA [Section 1.3]) to measure thymus and activation-regulated chemokine (TARC) will be identified by the participant number (coded) and retained at a facility selected by Lilly or its designee for a maximum of 1 year following the last participant visit for the study at a facility selected by Lilly or its designee.

## **8.7. Genetics**

A blood sample for DNA isolation will be collected from participants.

See [Appendix 5](#) for information regarding genetic research and Appendix 1 (Section 10.1.11) for details about sample retention and custody.

## **8.8. Biomarkers**

Biomarkers will not be evaluated in this study.

## **8.9. Immunogenicity Assessments**

At the visits and times specified in the SoA (Section 1.3), venous blood samples will be collected to determine antibody production against lebrikizumab. Antibodies may be further characterized for their ability to neutralize the activity of lebrikizumab. To interpret the results of immunogenicity, a venous blood sample will be collected at the same time points to determine the serum concentrations of lebrikizumab. All samples for immunogenicity should be taken predose when applicable and possible.

Upon assay validation, ADAs may be characterized; treatment-emergent ADAs (TE-ADAs) are defined in Section 9.4.6.

The purpose of retention, the maximum duration of retention, and facility for long-term storage of samples are described in Appendix 1 (Section 10.1.11). Samples may also be used for development and control of an immunogenicity assay.

## **8.10. Health Economics**

Not applicable.

## 9. Statistical Considerations

### 9.1. Statistical Hypotheses

The null hypothesis for the primary endpoint is that there is no difference between lebrikizumab 250 mg Q2W and placebo or lebrikizumab 250 mg Q4W and placebo in reducing the signs and symptoms of AD as measured by both the proportion of participants achieving IGA score of 0 or 1 and a reduction of  $\geq 2$ -points from baseline to Week 16 and the proportion of participants achieving EASI-75 ( $\geq 75\%$  reduction from baseline in EASI score) at Week 16.

### 9.2. Sample Size Determination

Approximately 280 participants will be randomized at a 3:2:2 ratio to lebrikizumab 250 mg Q2W, lebrikizumab 250 mg Q4W, or placebo (120 participants: 80 participants: 80 participants). The inclusion of approximately 15 adolescents is based on enrollment feasibility in Japan.

The assumed IGA score of 0 or 1 at Week 16 response rates are 38% for lebrikizumab 250 mg Q2W, 33% for lebrikizumab 250 mg Q4W, and 13% for placebo. The assumed EASI-75 response rates at Week 16 are 58% for lebrikizumab 250 mg Q2W, 53% for lebrikizumab 250 mg Q4W, and 20% for placebo. The assumptions for lebrikizumab are based on the DRM06-AD01 Phase 2b study, and the proportion of participants who achieved an IGA score of 0 or 1 and proportion of participants who achieved EASI-75 response at Week 16 using the rescue medication nonresponse sensitivity analysis, adjusting for the allowed use of TCS. The placebo response rate is based on the review of historical TCS clinical studies in AD (Simpson et al. 2016). This study has  $>95\%$  and  $>80\%$  power to test the superiority of lebrikizumab 250 mg Q2W to placebo and lebrikizumab 250 mg Q4W to placebo in the co-primary endpoints based on a two-sided Fisher exact test with alpha of 0.05.

### 9.3. Populations for Analyses

The following populations are defined:

Population	Description
Entered	All participants who signed informed consent/assent. Participant flow will be summarized.
Intent-to-Treat (ITT)	All randomized participants, even if the participant does not take the assigned treatment, does not receive the correct treatment, or otherwise does not follow the protocol. Participants will be analyzed according to the treatment group to which they were assigned. Unless otherwise specified, efficacy and health outcome analyses for the Induction Period will be conducted on this population.
Safety Population	All randomized participants who received at least 1 dose of study intervention during the Induction Period. Safety analyses for the Induction Period will be conducted on this population.

Population	Description
Per-Protocol Set (PPS)	All ITT participants who do not have a subset of important protocol deviations that impact the primary efficacy endpoint. Important protocol deviations are defined in a separate document referred to as "The KGAL Trial Issues Management Plan." Primary efficacy analysis for IGA 0/1 and EASI-75 will be repeated using the PPS.
Maintenance Period Primary Population	All participants who were randomized to lebrikizumab 250 mg Q2W at baseline visit and re-randomized to lebrikizumab 250 mg Q2W or lebrikizumab 250 mg Q4W (that is, participants who achieved an IGA of 0 or 1 and/or EASI-75 and were re-randomized at Week 16) or who were randomized to lebrikizumab 250 mg Q4W at baseline visit and continued lebrikizumab 250 mg Q4W (that is, participants who achieved an IGA of 0 or 1 and/or EASI-75 at Week 16) and received at least 1 dose of study intervention during the Maintenance Period. Participants will be analyzed according to the treatment to which they were assigned. Only information prior to escape will be presented. Efficacy, health outcome, and safety analyses for the Maintenance Period will be conducted primarily on the Maintenance Period Primary Population.
Maintenance Period Secondary Population	Participants who were randomized to placebo at baseline visit and participants who entered the Escape Arm at Week 16 due to not meeting IGA 0/1 and EASI-75 criteria or using rescue therapy during the Induction Period and received at least 1 dose of study intervention during the Maintenance Period. Selective efficacy analyses for the Maintenance Period will be conducted on the Maintenance Period Secondary Population.
Maintenance Period Escape Population	Maintenance Period Primary and Secondary Population who escaped to lebrikizumab 250 mg Q2W due to EASI-50 non-response at Weeks 20, 24, 28, 32, 36, 40, 44, 48, 52, 56, 60 or 64. Selective efficacy analyses for the Maintenance Period will be conducted on the Maintenance Period Escape Population to assess whether these participants re-gain EASI-50 response or achieve a higher level of response (for example, EASI-75) following re-treatment.

Population	Description
All Lebrikizumab Safety Population	All randomized participants who received at least 1 dose of lebrikizumab treatment during Combined Induction and Maintenance Periods. Safety analyses for the Combined Induction and Maintenance Periods will be conducted on the All lebrikizumab Safety Population. Selective safety analyses for the Combined Induction and Maintenance Periods plus the Follow-Up Period will be conducted on the All Lebrikizumab Safety Population.
Pharmacokinetic Analysis	All participants who received at least 1 dose of lebrikizumab and have at least 1 evaluable PK sample.

Abbreviations: EASI-75 =  $\geq 75\%$  reduction from baseline in Eczema Area and Severity Index IGA = Investigator's Global Assessment; Q2W = every 2 weeks; Q4 = every 4 weeks.

## 9.4. Statistical Analyses

### 9.4.1. General Considerations

Statistical analysis of this study will be the responsibility of the sponsor or its designee.

All tests of treatment effects will be conducted at a 2-sided alpha level of 0.05, unless otherwise stated, and all CIs will be given at a 2-sided 95% level.

For the efficacy and health outcome analyses during the Induction and Maintenance Periods, baseline is defined as the last available value before the first injection in the Induction Period. In most cases, this will be the value recorded at baseline visit (Visit 2, Week 0).

For safety analyses during the Induction Period, the Baseline Period is defined as the time from the screening visit (Visit 1) to the date/time of the first injection in the Induction Period. Baseline will be the last scheduled non-missing assessment recorded during the baseline period. Unless specified otherwise, for the safety analyses during the Maintenance Period, baseline is defined as the last available value before the first injection in the Maintenance Period. In most cases, this will be the measure recorded at Week 16.

Descriptive statistics will be used to provide an overview of the efficacy and safety results. For categorical parameters, the number and percentage of participants in each category will be presented. For continuous parameters, descriptive statistics will include number of participants (n), mean, SD, median, minimum, and maximum. Appropriate inferential statistics will be used for the primary and secondary efficacy variables.

The primary estimand that will be used to analyze primary and secondary endpoints is a composite variable strategy where comparisons will not include data collected after intercurrent events of changes to background therapies or discontinuation due to lack of efficacy (ICH E9 [R1]).

Any change to the data analysis methods described in the protocol will require an amendment only if it changes a principal feature of the protocol. Any other change to the data analysis methods described in the protocol, and the justification for making the change, will be described

in the statistical analysis plan (SAP) and the clinical study report. Additional exploratory analyses of the data will be conducted as deemed appropriate.

The SAP will be finalized prior to unblinding and it will include a more technical and detailed description of the statistical analyses described in this section. This section is a summary of the planned statistical analyses of the most important endpoints, including primary and key secondary endpoints.

#### **9.4.1.1. Missing Data Imputation**

The primary method of handling missing efficacy data after intercurrent events will be as discussed below for both binary and continuous endpoints.

For participants who receive rescue medication (high-/ultra-high-potency TCS or systemic AD treatment) or withdraw from the study due to lack of efficacy, the participant's baseline value will be carried forward to the subsequent time points through Week 16. Markov Chain Monte Carlo multiple imputation will be used to handle the remaining missing data.

Sensitivity analyses will be addressed in the SAP.

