#### 7.1.1. Criteria for Permanent Discontinuation of Study Intervention

##### Data collection and safety follow-up when study intervention is permanently discontinued

If study intervention is permanently discontinued, the participant will remain in the study to have an ET visit and posttreatment follow-up visits, as shown in the SoA (Section 1.3).

See the SoA (Section 1.3) for data to be collected at the time of discontinuation and follow-up and for any further evaluations that need to be completed. Safety follow-up is as outlined in the SoA (Section 1.3) and in Section 8.2 ("Safety Assessments) and Section 8.3 ("Adverse Events and Serious Adverse Events") of the protocol.

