1.1.1. Estimands

1.1.1.1. Primary and Supportive Estimands for Induction Period

There will be three estimands of interest in analyzing primary and key secondary endpoints for the Induction Period. Two types of intercurrent events in terms of estimating the treatment effects for the Induction Period will be considered: initiation of rescue medication as defined in Section 6.6.1 and permanent treatment discontinuation.

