1.1.1.1.1. Primary Estimand (Hybrid)

The primary estimand is a hybrid estimand representing the primary clinical question of interest: what is the difference between treatment conditions, i.e., Lebrikizumab vs Placebo, in the target participant population, in successful responses or means after 16 weeks achieved without use of rescue medication and if all participants continued with treatment except those who discontinued due to lack of efficacy?

The primary estimand is described by the following attributes:

- Population: defined through appropriate Inclusion/Exclusion (I/E) criteria to reflect the targeted participant population for approval
- Endpoint: apply to all primary and key secondary endpoints
- How to account for intercurrent events (ICEs)

- a. Participants who require any use of rescue medication or discontinued treatment due to lack of efficacy prior to Week 16 will be considered as treatment failures, i.e., non-responder, after the ICEs. Therefore, composite strategy is used for these types of ICEs.
- b. For participants who discontinue treatment due to reasons other than lack of efficacy prior to Week 16, a hypothetical strategy will be used to estimate what the treatment effect would have been if participants continued with treatment. Therefore, hypothetical strategy is used for these types of ICEs.

D. Population-level summary: difference in response proportions or means between treatment conditions

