4.1.6.1.1. Markov Chain Monte Carlo Multiple Imputation (MCMC-MI)

The primary method of handling missing efficacy data relative to the primary estimand will be as follows for both binary and continuous endpoints:

For participants who receive rescue medication (i.e., high-potency TCS or systemic AD treatment, defined in [Appendix 13](#)), or discontinue treatment due to lack of efficacy, set to the participant's baseline value subsequent to this time through Week 16. The MCMC-MI will be used to handle the remaining missing data. Imputation will be conducted within each treatment group independently so the pattern of missing observations in one treatment group cannot influence missing value imputation in another. The SAS PROC MI with MCMC option will be used to conduct the MCMC-MI. The imputation model will include the relevant baseline and post-baseline.

For each imputation process, 25 datasets with imputations will be calculated. The initial seed values are given in the table below. Each complete data set will be analyzed with the specified analysis. The results from these analyses will be combined into a single inference using SAS PROC MIANALYZE.

CMH test statistic will be transformed using the Wilson-Hilferty transformation and then standardized (Ratitch 2013) prior to combining them using SAS PROC MIANALYZE. Details of combining estimates and test statistics for categorial endpoints with multiple imputation can be found in [Appendix 14](#).

For binary responses related to EASI and IGA, the binary response variables will be calculated based on the multiply imputed datasets that have been created. Because the MCMC algorithm is based on the multivariate normal model, imputed values for IGA will not generally be one of the discrete values used in IGA scoring (0, 1, 2, 3, or 4). Therefore, to derive the binary IGA response variable, standard rounding rules will be applied to the imputed values. For example, if a participant has an IGA score imputed as 1.4 (and assuming a Baseline IGA score of 3), the imputed value would be rounded down to 1, and the minimum change from Baseline of 2 would have been met. This participant would be considered a responder.

For derivation of an EASI-75 and EASI-90 response, no rounding will be performed. The imputed Week 16 EASI value will be compared directly to the observed Baseline EASI value to determine whether a reduction of at least 75% or 90% was achieved.

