4.1.6.1.2. Tipping Point Analyses

The co-primary endpoints of EASI-75 and IGA score of 0 or 1 with ≥ 2 -point improvement from baseline at Week 16 and the following key secondary endpoints: EASI-90 at Week 16 and Itch NRS improvement ≥ 4 -point, at Week 16 will be assessed using the tipping point analysis. For

each of these endpoints, the tipping point analysis will only be conducted if its co-primary or key secondary analyses results are statistically significant.

All participants who use rescue medication or discontinue treatment due to lack of efficacy will be imputed as non-responders. Assumptions on missing data as a result of treatment discontinuation due to reasons other than lack of efficacy or any other intermittent missing data will be varied to investigate if there will be any tipping points.

For all the categorical endpoints described above that will be assessed using tipping point analysis, the following process will be used to determine the tipping point:

- Missing responses in the lebrikizumab groups will be imputed with a range of response probabilities, including probabilities of 0, 0.2, 0.4, 0.6, 0.8, and 1.0.
- For missing responses in the placebo group, a range of response probabilities (for example, probability = 0, 0.2 ... 1.0) will be used to impute the missing values. Multiple imputed dataset will be generated for each response probability.
- Treatment differences between lebrikizumab and placebo are analyzed for each imputed dataset using CMH test (Section 4.1.1). Results across the imputed datasets are aggregated using SAS PROC MIANALYZE in order to compute a p-value for the treatment comparisons for the given response probability. If the probability values do not allow for any variation between the multiple imputed datasets (for example, all missing responses in the placebo and lebrikizumab groups are imputed as responders and non-responders, respectively, i.e., extreme case), then the p-value from the single imputed dataset will be used.

The tipping point is identified as the response probability value within the placebo group that leads to a loss of statistical significance when evaluating lebrikizumab relative to placebo.

For tipping point analyses, the number of imputed data sets will be $m=25$ and the seed values to start the pseudorandom number generator of SAS are given in the table below.

Seed Values for Tipping Point Analysis

Analysis	Seed value

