4.3.2. Main analytical approach

The primary analysis of the study is to test the co-primary null hypotheses described in Section 2 in the ITT Population.

The primary estimand addresses the treatment response as directed. The analysis assumes that treatment response disappears for participants who took rescue medication (i.e., high-potency TCS or systemic AD treatment, defined in [Appendix 13](#)) or withdrew from the study due to lack of efficacy, therefore setting to the participant's baseline value subsequent to this time through

Week 16. Other missing values will be imputed using MCMC-MI based on missing at random assumption (Section 4.1.6.1.1).

A CMH test as described in Section 4.1.1 will be used for the comparisons. The OR, the corresponding 95% CIs and p-value, as well as the treatment differences and the corresponding 95% CIs, will be reported.

Multiplicity controlled analyses will be performed on the primary and key secondary endpoints to control the overall Type I error rate at a 2-sided alpha level of 0.05. A graphical approach will be used to perform the multiplicity controlled analyses as described in Section 2.1.

The analyses for primary outcomes of EASI-75 and IGA score of 0 or 1 are described in [Appendix 2](#).

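### SAP 4.3.2 and Protocol 9.4.1.1 reset co-primary values to baseline on study withdrawal for lack of efficacy; the SAP's estimand, imputation and tipping-point sections do so on treatment discontinuation

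*Protocol*

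**What the plan says.** Two triggers are written for the same reset to baseline.

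- **Study withdrawal.** Protocol 9.4.1.1 applies it to rescue users and to those who "withdraw from the study due to lack of efficacy". SAP 4.3.2, which sets out the main analysis of the co-primary endpoints, applies it to those who took rescue or "withdrew from the study due to lack of efficacy". Both send the remaining missing values to MCMC multiple imputation; 4.3.2 adds that this assumes missing at random.
- **Treatment discontinuation.** SAP 1.1.1.1 names the Induction intercurrent events as "initiation of rescue medication as defined in Section 6.6.1 and permanent treatment discontinuation"; study withdrawal is not among them. SAP 1.1.1.1.1 says of rescue users that they, and those who "discontinued treatment due to lack of efficacy prior to Week 16 will be considered as treatment failures", are non-responders afterwards, and the summary table of Induction estimands matches. SAP 4.1.6.1.1 resets those who "discontinue treatment due to lack of efficacy". SAP 4.1.6.1.2 says: "All participants who use rescue medication or discontinue treatment due to lack of efficacy will be imputed as non-responders".

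The estimand sentence in Protocol 9.4.1 speaks only of discontinuation, without saying from what. SAP 4.9 lists two changes from the protocol, and neither concerns this trigger.

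**The concern.** Stopping treatment and leaving the study are separate events in this protocol. Under Protocol 7.1.1, when study intervention is permanently stopped, "the participant will remain in the study to have an ET visit and posttreatment follow-up visits". Under 7.2, leaving the study also ends study intervention, but the reverse does not follow. Protocol 9.4.2.1 summarizes reasons for the two separately, and SAP 4.2 counts them separately by site. Someone programming from 4.3.2 would look for a study-withdrawal reason; someone programming from 4.1.6.1.1 would look for a treatment-discontinuation reason.

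Followed literally, 4.3.2 sends some participants whom the estimand calls failures to missing-at-random imputation. It would also leave the primary analysis and its tipping-point sensitivity analysis disagreeing about who counts as missing, so the tipping point would no longer vary the missing-data assumption alone.

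**Working it through.** **Which participants are classified differently**

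| Participant in the Induction Period | Study-withdrawal trigger | Treatment trigger |
|---|---|---|
| Uses rescue | Baseline value, non-responder | Baseline value, non-responder |
| Leaves the study for lack of efficacy, so also stops treatment (7.2) | Non-responder | Normally non-responder |
| Stops treatment for lack of efficacy, no rescue, no study withdrawal recorded for that reason, Week 16 missing | MCMC-MI within arm; may be a responder | Non-responder in all 25 imputed datasets |
| Stops treatment for another reason, Week 16 missing | MCMC-MI | MCMC-MI |

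Only the third row differs. An imputed value can count as a response: SAP 4.1.6.1.1 gives the example of an IGA imputed as 1.4, rounded to 1 and scored as a responder from a baseline of 3.

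**The plan's own figure**

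Inputs (Protocol 9.2, SAP 5): arms of 120, 80 and 80 (Q2W, Q4W, placebo); IGA 0/1 rates 38%, 33% and 13%; EASI-75 rates 58%, 53% and 20%; two-sided Fisher exact test at 0.05. Exact power is the sum, over all pairs of responder counts, of the product of the two binomial probabilities wherever Fisher's p is at most 0.05. Joint power for two endpoints with powers a and b lies between a + b − 1 and min(a, b).

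- Q2W: IGA 97.95%, EASI-75 99.98%, joint about 97.9%. Stated: above 95%.
- Q4W: IGA 82.5%, EASI-75 99.1%, joint 81.6% to 82.5%. Stated: above 80%.

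Both statements reproduce, and neither depends on the trigger wording.

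**Effect per affected participant**

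If the imputed response probability equals the planned rate p, one participant adds p/n to the arm's rate:

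- Q2W: 0.38/120 = 0.32 points (IGA), 0.58/120 = 0.48 (EASI-75)
- Q4W: 0.33/80 = 0.41, 0.53/80 = 0.66
- Placebo: 0.13/80 = 0.16, 0.20/80 = 0.25

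**Effect on the treatment difference**

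Assumptions: a share d of an arm falls in the third row; the planned rate p holds under the treatment trigger; imputation gives these participants the response rate of the rest of the arm, p/(1 − d). The arm's rate then rises by d × p/(1 − d). Example for EASI-75, Q2W, d = 5% in both arms: 0.05 × 0.58/0.95 − 0.05 × 0.20/0.95 = 3.05 − 1.05 = 2.00 points.

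Change in the lebrikizumab-placebo difference, in percentage points, on moving from the treatment trigger to the study trigger:

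| d on lebrikizumab / placebo | IGA Q2W | IGA Q4W | EASI-75 Q2W | EASI-75 Q4W |
|---|---|---|---|---|
| 1% / 1% | +0.25 | +0.20 | +0.38 | +0.33 |
| 2% / 2% | +0.51 | +0.41 | +0.78 | +0.67 |
| 5% / 5% | +1.32 | +1.05 | +2.00 | +1.74 |
| 1% / 5% | −0.30 | −0.35 | −0.47 | −0.52 |
| 2% / 10% | −0.67 | −0.77 | −1.04 | −1.14 |

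The sign turns where d/(1 − d) on placebo exceeds that on lebrikizumab by the ratio of the planned rates: 0.38/0.13 = 2.9 (IGA) and 0.58/0.20 = 2.9 (EASI-75) for Q2W; 0.33/0.13 = 2.5 and 0.53/0.20 = 2.65 for Q4W.

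As an illustration only, exact power for Q4W IGA at the shifted rates goes from 82.5% to 80.3% in the fourth row and 77.7% in the fifth.

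**The case against.** The strongest reply is that the operative rule can be identified. SAP 4.3.2 refers to 4.1.6.1.1 for the imputation; that section is the method, and it uses the treatment trigger. The intercurrent-event list, the estimand, its table, the tipping-point section and the COVID-19 appendix all speak of treatment. Protocol 9.4.1 describes its statistical section as a summary, with technical detail left to the SAP, and requires an amendment only for a principal feature. This largely stands: the two wordings do not have equal weight, and a careful programmer would probably choose the treatment trigger. It does not make 4.3.2 correct, because the section that governs the co-primary analysis still states the other event. Protocol 9.4.1 also asks for changes to its methods to be described and justified in the SAP and study report.

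The planned supplementary analysis with non-responder imputation makes every treatment discontinuation a non-response, and the tipping-point analysis uses the treatment trigger. These would show whether the choice matters, but they do not settle which rule is primary.

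A reader might infer three stronger things that the documents do not support.

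- *That the SAP contradicts itself on the major secondaries too.* SAP 4.4.1.2 sends those to Appendix 2, which names the primary estimand with MCMC-MI, and 4.1.6.1.1 expressly covers EASI-90, EASI percentage change and Itch NRS. Only Protocol 9.4.1.1 differs for them.
- *That Protocol 7.2 leaves no lack-of-efficacy route out of the study during Induction.* It allows withdrawal at the participant's own request and when another effective agent is needed. The disposition reason codes are not shown, so how a given non-responder would be recorded is unknown.
- *That the study trigger necessarily favours lebrikizumab, with a ceiling of 1.9 points.* The direction depends on where the stops fall. The 1.9 comes from share times planned rate, 0.05 × (58 − 20); imputing at the rate of the rest of the arm gives 2.0, so it is no ceiling.

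**Conclusion.** The inconsistency is real and should be corrected. As written, SAP 4.3.2 and Protocol 9.4.1.1 would treat as ordinary missing data some participants whom the SAP's primary estimand calls treatment failures. The conflict runs one way, affects only those who stop treatment for lack of efficacy without rescue and without a study withdrawal recorded for that reason, and within the SAP is confined to the co-primary section.

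The group is probably small. The documents give no stop rate, so size and direction both rest on assumption: the difference widens by about 0.2 to 2.0 points if 1% to 5% are affected equally in all arms, and narrows by about 0.3 to 1.1 points with 1% to 2% on lebrikizumab and 5% to 10% on placebo. Poor scores recorded before the stop would lower the imputed response probability and shrink either shift. The documents do not support saying that the trial's result turns on the wording, or that the stated power is wrong.

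**What to change.** In SAP 4.3.2, replace "withdrew from the study due to lack of efficacy" with the trigger used in 4.1.6.1.1, "discontinue treatment due to lack of efficacy" (in the past tense), and name the treatment-disposition reason as its source. Then either make the same change in Protocol 9.4.1.1, stating in the 9.4.1 estimand sentence that discontinuation means discontinuation of study intervention, or add a line to SAP 4.9 declaring and justifying the departure. Do this before unblinding.

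The cost is one phrase and one line of text, with no new data. Response rates may come out slightly lower than under the study-withdrawal wording.
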